## **INTRODUCTION**

During the course of orthodontic treatment, the practitioner faces two common iatrogenic treatment side effects, root resorption and enamel decalcification, with the latter occurring at a much higher frequency. While the processes that lead to enamel demineralization are understood, methods to diminish or perhaps eliminate degradation of enamel surfaces are being searched for. Several approaches have been formulated to counteract demineralization of tooth structure. One approach involves patient compliance and consists of in-depth oral hygiene instructions, in-office fluoride applications, and at-home fluoride rinses, gels and varnishes. An alternative approach, which possesses potential benefit regardless of patient compliance includes the use of fluoride-releasing agents, such as composites, glass ionomers, sealants, and elastomeric ties.

Enamel decalcification or white spot formation, is a phenomenon occurring primarily on smooth enamel surfaces of teeth, notably within the gingival third of the crown. Demineralized enamel, the precursor to caries formation, can be attributed to fixed orthodontic appliances, and prolonged exposure to bacterial plaque. Bacterial plaque promotes the accumulation of acidic byproducts and demineralization that leads to successive changes in the optical properties of subsurface demineralized enamel. Progression to clinically detectable white spot lesions may occur as early as one month following the placement of orthodontic appliances.

Over the past thirty years, numerous studies have reported an increase in white spot lesions following orthodontic treatment. While a large portion of the non-orthodontically-treated population experiences some form of decalcification, orthodontically-treated patient populations have shown both an increase in new lesions and an increase in the severity of preexisting enamel opacities. Approximately, 50 percent of orthodontically-treated patients develop white spot

lesions in one or more teeth, compared with only 24 percent in those not undergoing orthodontic treatment.

Appliance removal halts white spot formation and further elimination of cariogenic factors through diligent oral hygiene efforts inactivates incipient lesions, which may undergo regression over time. Complete elimination of lesions is unlikely due to the rapid remineralization of the enamel surface with high concentration fluorides, which restrict passage of ions into the deeper more affected layers. Therefore, immediate application of high concentration of fluoride is not recommended. Decreased enamel discolorations may occur with time due to further remineralization, but regression is primarily credited to gradual surface abrasion of tooth structure.

Such problems with enamel decalcification in orthodontic patients have influenced clinicians to search for a solution to orthodontic-associated demineralization. Because fluoride treatment immediately upon debonding is not advocated, clinicians have proposed fluoride treatment and fluoride-releasing materials at the commencement of therapy. Recommended solutions include oral hygiene instruction and reinforcement, fluoridated toothpastes, varnishes and mouthwashes, and fluoridated water supply. Lack of patient compliance hinders these efforts.

A new product, MI Varnish is current available and has been shown in some initial case reports to be useful in the reduction of white spot lesions. MI Varnish is a one-of-a-kind product that restores minerals and helps you produce saliva. It's the only dental product with RECALDENT™ (CPP-ACP), a special milk-derived protein that's a breakthrough in oral health care in helping to remineralize teeth.

- Strengthens teeth with tooth-replenishing calcium and phosphate
- Releases vital minerals into your mouth when and where they're needed
- Produces a saliva-like environment that maintains normal acid levels and healthy teeth
- Recaldent™ CPP-ACP is milk derived with lactose content less than 0.01%.\*

## **AIM**

To determine if MI Varnish has an effect in preventing the formation of white spot lesions for patients undergoing orthodontic treatment.

## **MATERIALS AND METHODS**

## **Subjects**

33 subjects were prospectively recruited for the project in the MI Varnish group. These subjects were studied against a control group of 29 orthodontically treated subjects who received routine treatment and oral hygiene regimes. All subjects will be patients seeking orthodontic treatment at the Department of Orthodontics, School of Dentistry, University of Alabama at Birmingham. A caries risk assessment (Information attached) will be used to determine the caries risk of all patients enrolled in the study.

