Statistical Analysis Plan

Title of Research: The Use of MI Varnish for the Prevention and Reduction of White Spot Lesions in

Orthodontic Treatment

WIRB Protocol #: 20120677

Principal Investigator: [name] [name], BDS, MScD, PhD.

Document Date: January 1, 2018

Results and Statistics

The results will be evaluated in the following manner:

(1) Difference in prevention of white spot formation between the control and the study groups using the EDI scores

(2)Standard statistical methods were employed to analyze all data.

Data Collection and Database Management

Data collection, database management, and data analyses were performed by sponsor personnel or its designee. Only the sponsor, or its appropriate designee, had access to individual-level patient data collected as part of this study, regardless of whether the patient provided informed consent and HIPAA authorization. All individual level patient data had identification information removed.

Data Analysis

All measured variables and derived parameters will be tabulated by descriptive statistics.

For categorical variables summary tables will be provided giving sample size, absolute and relative frequency and 95% CI (Confidence Interval) for proportions.

For continuous variables summary tables will be provided giving sample size, arithmetic mean, standard deviation, median, minimum and maximum and 95% CI (Confidence Interval) for means of variables.

All tests will be two-tailed, and a p value of 5% or less will be considered statistically significant.

All statistical analyses will be performed and data appendices will be created using the SAS® system Version 9.1.3 or higher.

The effects of noncompliance, dropouts, and covariates on treatment will be assessed to determine the impact on the general applicability of results from this study.

[figure not shown]

Figure 1. Enamel Decalcification Index. Facial surface of each tooth was divided into four areas. A score was allocated for each area of each tooth: 0=No decalcification to 3=Decalcifications covering 100% of the area.

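### No random allocation is described, and the SAP does not commit to adjusting the EDI comparison for the caries risk assessed on every patient

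*Protocol*

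**What the plan says.** **How the groups arose.** The Protocol (Subjects) states: "33 subjects were prospectively recruited for the project in the MI Varnish group". It continues: "These subjects were studied against a control group of 29 orthodontically treated subjects who received routine treatment and oral hygiene regimes". All subjects come from one orthodontic department. Neither document mentions randomisation, matching, stratification or whether the controls were concurrent.

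**Caries risk.** The same section plans: "A caries risk assessment (Information attached) will be used to determine the caries risk of all patients enrolled in the study". It gives no timing, and neither document gives the result a role in forming or analysing the groups.

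**The comparison.** The SAP (Results and Statistics) names one treatment comparison: "Difference in prevention of white spot formation between the control and the study groups using the EDI scores". The method is: "Standard statistical methods were employed to analyze all data". No test, model, covariate, patient-level summary or visit is named. Under Figure 1, however, "A score was allocated for each area of each tooth", and the Protocol (Re-call) has two visits at four-week spacing and then three-monthly ones.

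**Covariates.** The only provision is in the SAP (Data Analysis): the "effects of noncompliance, dropouts, and covariates on treatment will be assessed to determine the impact on the general applicability of results".

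**The concern.** With random allocation, an unadjusted comparison has the right error rate and adjustment mainly buys precision. Without it, nothing makes the groups comparable. Caries risk is an obvious prognostic factor for this outcome: the Protocol's own introduction describes demineralised enamel as what precedes caries. If the controls carried more high-risk patients, an inert varnish would look protective. If the varnish group carried more, a real benefit could be missed.

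The trial plans to assess this factor on everyone, so the means of addressing it is within reach. The SAP neither commits to using it nor limits the conclusion if it is not used.

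**Working it through.** The plan states no sample-size calculation, effect size or EDI variance, so it has no figure to reproduce. The documents supply only the group sizes (33 and 29), the two-sided 5% level and, for step 4, a lesion rate of about 50% in orthodontic patients. Everything else below is assumed, to show the mechanism.

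**1. Spurious difference and its standard error.** Let high caries risk raise EDI by *d* (in units of the SD within a risk category), with high-risk shares p_V (varnish) and p_C (control) and no varnish effect. Then

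- spurious difference = d × (p_C − p_V)
- SE ≈ √[(1 + d²·p(1−p)) × (1/33 + 1/29)], with 1/33 + 1/29 = 0.0648

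For d = 0.8:

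- 40/60: difference 0.8 × 0.20 = 0.16; SE = √[(1 + 0.64 × 0.24) × 0.0648] = 0.273; ratio 0.585; rejection about 9.0%.
- 30/70: difference 0.8 × 0.40 = 0.32; SE = √[(1 + 0.64 × 0.21) × 0.0648] = 0.271; ratio 1.18; rejection about 21.9%.

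**2. Simulation (100,000 trials per cell).** It gives 8.9% and 21.5% for these two cells. False-positive rates in full:

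| d (SD) | Analysis | 45/55 | 40/60 | 30/70 |
|---|---|---|---|---|
| 0.5 | Unadjusted | 5.4% | 6.7% | 11.6% |
| 0.5 | Adjusted, 20% misclassified | 5.1% | 5.7% | 8.1% |
| 0.8 | Unadjusted | 5.8% | 8.9% | 21.5% |
| 0.8 | Adjusted, 20% misclassified | 5.4% | 6.8% | 12.6% |
| 1.0 | Unadjusted | 6.5% | 10.9% | 29.2% |
| 1.0 | Adjusted, 20% misclassified | 5.7% | 7.4% | 16.1% |

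At 50/50 the unadjusted rate is 5%. Adjusted for risk measured without error, it is 4.8% to 5.1% in every cell.

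**3. Limits of adjustment (d = 0.8).**

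- *Misclassified risk.* At 40/60 the bias falls from 0.160 to 0.104 with 20% of patients in the wrong category (1 − 0.104/0.160 = 35% removed), and to 0.059 with 10% wrong (63% removed). At 30/70 it falls from 0.320 to 0.219 (32%) and 0.128 (60%).
- *A second, unmeasured confounder of equal size and imbalance.* The rate is 19% unadjusted and 8.6% adjusted at 40/60; 59% and 18% at 30/70.
- *Skewed scores (negative binomial, 17% to 33% zeros).* Unadjusted 4.8–5.8%, 5.7–9.5% and 9.5–25% at the three imbalances; adjusted 4.3–5.2% across all cells, including 50/50.

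**4. The opposite direction.** This uses any lesion yes/no, by exact binomial enumeration; it is not the EDI. Assume lesion rates of 70% (high risk) and 30% (low risk), and a varnish that halves them. Power is 58.5% with balanced groups. It falls to 38.9% if the varnish group has 60% high-risk patients against 40% in controls, and to 22.1% at 70% against 30%.

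**5. How unusual are such gaps?** Under randomisation, with half the patients at high risk, a gap of 20 points or more arises with probability 0.115, and 40 points or more with probability 0.0014. The 30/70 column therefore needs strong selection.

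**The case against.** The harm needs two things that the documents do not establish: non-random allocation and an imbalance in caries risk. Silence does not prove the first. Some pages and the caries-risk attachment are not in the public text, and drawing everyone from one department gives some similarity of source. The SAP does have a covariate sentence, which does not rule out an adjusted estimate. All the sizes are assumed. At 40/60 and 0.5 SD the excess is under two points, and with 20% misclassification adjustment only takes 6.7% to 5.7%. Where imbalance is large, other confounders are likely, so adjustment is least sufficient where it is most needed.

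All of this stands as a limit on size and certainty. It does not supply the missing commitment. A single department does not show concurrent or random assignment. The covariate sentence names no covariate or model, and its stated purpose is applicability, not bias in the EDI difference.

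Two further points should carry into the fix. Without an EDI at bonding, a follow-up score mixes pre-existing with new lesions, and caries-risk adjustment does not separate them. The Protocol (Photographic records) uses the index for the number of lesions, while SAP Figure 1 scores the area affected. Finally, the SAP uses the past tense in places ("Data collection, database management, and data analyses were performed by sponsor personnel or its designee"), so a model specified now may be post hoc.

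**Conclusion.** The point holds, with medium confidence, and should be fixed. No allocation method is described, and the SAP does not commit to adjusting its one treatment comparison for caries risk. If allocation was random, the unadjusted test is valid and one documenting sentence removes the concern about bias. If it was not, the prevention conclusion could be biased in either direction by an amount the documents do not allow anyone to calculate.

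On the stated assumptions, the false-positive rate barely moves with small imbalances (5.4% to 6.5% at 45/55). It reaches 6.7% to 11% at 40/60 and 12% to 29% at 30/70. Adjustment returns it to 5% only if caries risk is the sole confounder and is measured without error.

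**What to change.** **In the Protocol:** state how and when the 29 controls were obtained, how patients came to be in each group, and when caries risk was assessed.

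**In the SAP:**

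- Make the main estimate a regression of one stated patient-level EDI summary (for example the mean area score over scored teeth) at one stated recall visit, on group and caries-risk category. This requires that risk was assessed in both groups before or at bonding. Reconcile the chosen summary with the Protocol's lesion count.
- Add EDI at bonding if it was recorded; neither document says it was. If it was not, state that the outcome includes pre-existing lesions.
- Report the adjusted difference with its 95% CI, robust or bootstrap if scores are skewed, and the unadjusted difference as secondary.
- Rewrite the covariate sentence to name the covariate and the model.
- Label the adjusted analysis post hoc if outcome data had already been seen.
- Unless random allocation is documented, describe the result as a non-randomised comparison, with residual bias possible from misclassified risk or unmeasured factors.

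**Cost:** wording, one model, and one or two degrees of freedom (two or three risk categories) out of 62 subjects. In balanced groups the SE of the group difference is 2% to 10% smaller if risk shifts EDI by 0.5 to 1.0 SD (0.261 to 0.256; 0.284 to 0.256), but only 0% to 3% smaller with 20% misclassification. If risk is unrelated to EDI and has two categories, the SE is 1% to 3% larger for gaps up to 20 points and 11% larger at 30/70 (0.253 to 0.281). With three categories it is 2%, 5% and 18% larger for gaps of 0, 20 and 40 points. The conclusion also becomes more cautious.

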## **Varnish Delivery**

The study group received the MI Varnish on the day of bracket bonding. The varnish was delivered all around the bracket and left for 15 minutes. Patients did not rinse after they received treatment.

## **Re-call**

Subjects were recalled at initially for 4 weeks (twice) and then 3 monthly intervals.

## **EVALUATION OF RESULTS**

The following two forms of evaluations will be carried out:

- (a) Photographic records
- (b) Clinical examination

### *Photographic records*

Photographic records will be used to determine the improvements in the white spot lesions. A standard intra-oral photographic camera will be utilized and the photographs will be taken in a light controlled environment and photographs will be captured in a pre-set photographic protocol. The Enamel decalcification index (Banks and Richmond) – FIG 1 will be used to determine the number of white spot lesions present at each time frame. This method has been used successfully by Robertson and [name] et al (American Journal of Orthodontics and Dentofacial Orthopedics – In press)

Statistical Analysis Plan

Title of Research: The Use of MI Varnish for the Prevention and Reduction of White Spot Lesions in

Orthodontic Treatment

WIRB Protocol #: 20120677

Principal Investigator: [name] [name], BDS, MScD, PhD.

Document Date: January 1, 2018

Results and Statistics

The results will be evaluated in the following manner:

(1) Difference in prevention of white spot formation between the control and the study groups using the EDI scores

(2)Standard statistical methods were employed to analyze all data.

Data Collection and Database Management

Data collection, database management, and data analyses were performed by sponsor personnel or its designee. Only the sponsor, or its appropriate designee, had access to individual-level patient data collected as part of this study, regardless of whether the patient provided informed consent and HIPAA authorization. All individual level patient data had identification information removed.

Data Analysis

All measured variables and derived parameters will be tabulated by descriptive statistics.

For categorical variables summary tables will be provided giving sample size, absolute and relative frequency and 95% CI (Confidence Interval) for proportions.

For continuous variables summary tables will be provided giving sample size, arithmetic mean, standard deviation, median, minimum and maximum and 95% CI (Confidence Interval) for means of variables.

All tests will be two-tailed, and a p value of 5% or less will be considered statistically significant.

All statistical analyses will be performed and data appendices will be created using the SAS® system Version 9.1.3 or higher.

The effects of noncompliance, dropouts, and covariates on treatment will be assessed to determine the impact on the general applicability of results from this study.

[figure not shown]

Figure 1. Enamel Decalcification Index. Facial surface of each tooth was divided into four areas. A score was allocated for each area of each tooth: 0=No decalcification to 3=Decalcifications covering 100% of the area.
